3.2.5 Last Visit during the Treatment Period

The Last Visit for an assessment is the last non-missing assessment during the Treatment Period. All scheduled and unscheduled assessments within the Treatment Period will be considered. Last Visit will be determined separately each study assessment. Last Visit during the Treatment Period will be included in the by-visit summary unless noted otherwise.

3.3 Definition of Baseline values

3.3.1 Baseline for variables based on seizure count

Baseline values for seizure frequency variables will be derived from diary data recorded by the subject during the 4-week Baseline Period. This diary is collected at the Baseline Visit (Visit 2, Day 1). The Baseline value will be the seizure frequency per 28 days during the Baseline Period and is defined as the number of seizures standardized to a 28-day baseline period. It is computed for each subject as the number of seizures recorded over the subject's baseline diary period, divided by the subject's total number of non-missing days in that period, multiplied by 28. See details for calculation of seizure frequency in Section 8.1.1.1.

3.3.2 Baseline for other variables

Unless otherwise specified, the last valid measurement before the first study medication administration will be used as the Baseline value, including the pre-dose assessments on the day of Visit 2. Unless otherwise stated, if a Baseline visit measurement is missing, and a Screening visit measurement is available, the most recent Screening value will be utilized as Baseline. Both

scheduled and unscheduled Screening visits will be considered. If a scheduled Baseline assessment is taken on the same day as first administration of study medication and no time is collected, it will be assumed to have been taken prior to study medication. The time point used for Baseline will be determined separately for each variable. An exception is blood pressure, where a complete set of both systolic and diastolic blood pressure should be selected for baseline. Baseline values for PK evaluations included in this SAP is defined in Section 9.

3.4 Protocol deviations

Important protocol deviations (IPD) are those deviations from the protocol identified by the study team as important which will be summarized in the clinical report, in accordance with ICH E3. The criteria for identifying important protocol deviations will be defined within the appropriate protocol-specific document at study start. All protocol deviations will be reviewed periodically through the study as part of the ongoing data cleaning process and those identified as important will be documented prior to unblinding and integrated into the clinical database.

3.5 Analysis sets

Primary and secondary efficacy endpoints will be analyzed using the Full Analysis Set (FAS). Safety variables will be analyzed using the Safety Set (SS). Pharmacokinetic data listings will use the Pharmacokinetic Set (PKS).

These analysis sets are described below.

3.5.1 Enrolled Set

The Enrolled Set (ES) consists of all subjects who have given informed consent.

3.5.2 Randomized Set

The Randomized Set (RS) consists of all subjects randomized into the study; this includes all subjects who have a randomization number issued by the IRT, even if misrandomized.

3.5.3 Safety Set

The Safety Set (SS) consists of all subjects who were administered at least 1 dose or a partial dose of IMP based on the first dose date from the First Administration of Study Medication CRF. The SS will be used to summarize and analyze all safety variables. In case of dosing administration error, summaries and analyses using the SS will be conducted according to actual treatment administered.

3.5.4 Full Analysis Set

The Full Analysis Set (FAS) consists of all subjects in the RS who were administered at least 1 dose or a partial dose of IMP and have Baseline and at least 1 post-Baseline seizure frequency data during the Treatment Period. In case of dosing administration error, or change in treatment dose, summaries and analyses will be conducted according to randomized treatment. The FAS will be the primary analysis set for all efficacy summaries and analyses.

3.5.5 Per Protocol Set

Due to the early termination of the study, and the change in the , the Per Protocol Set (PPS) will not be included in the study.

3.5.6 Completer Set

The Completer Set is a subset of the FAS, consisting of those subjects who completed the 16-week treatment period.

3.5.7 Other analysis sets

3.5.7.1 Pharmacokinetic Set

The Pharmacokinetic Set (PKS) consists of those subjects who provide at least 1 PSL plasma concentration measurement. Note that it is possible for a subject in the PK-Set to have missing data for some evaluations (such as of the primary [REDACTED] metabolite).

3.6 Treatment assignment and treatment groups

At Baseline, eligible subjects will be randomly assigned to treatment regimens as described in Section 2.3. Prior to unblinding, the study team should identify and review all cases in which subjects received an incorrect study drug (dosing errors resulting in treatment crossover). Note that while dispensing errors can be identified prior to unblinding, actual treatment crossovers can only be identified via IRT report (only identifying the subject number), or after unblinding.

The FAS will be the primary analysis set for all efficacy summaries and analyses. Treatment crossover Subjects (including any subjects with dosing errors) will be analyzed for efficacy according to their randomized treatment assignment and not the actual treatment received.

Safety analyses will be based on the SS. It is expected that subjects will receive the randomized treatment and be analyzed according to that assigned treatment. However, if a subject were to experience a dosing error resulting in treatment crossover, incorrectly treated subjects will be evaluated during the blinded data evaluation meetings to assess the potential impact of such cases and any special considerations for statistical analyses.

3.7 Sites pooling strategy

Since “site” per se is not considered as a factor in the planned analyses there is no strategy in place for pooling data from sites with low number of patients to another particular site. Data will be combined across all sites within region, according to the specified analysis. To ensure at least 5 subjects in each region in the FAS at each treatment group, Japan will be pooled with North America to form a non-Europe region for the efficacy analyses.

3.8 Coding dictionaries

All prior and concomitant medications other than study drug will be classified by World Health Organization WHO Anatomical Therapeutic Chemical (ATC) Classification, presenting Anatomical Main Group (ATC Level 1), Pharmacological Subgroup (ATC level 3), and

preferred term, using Version SEP/2015 or higher of the World Health Organization Drug Dictionary (WHO-DD). Coding will be performed in accordance with UCB standard operating procedures (SOP).

Medical history and AEs will be coded by primary system organ class (SOC), high level term (HLT) and preferred term (PT) using version 22.1 or higher of Medical Dictionary for Regulatory Activities (MedDRA®) according to UCB Standard Operating Procedures (SOP).

3.9 Changes to protocol-defined analyses

Due to Covid-19 impact on site initiation and enrollment and due to early termination of the study, the following items in the protocol were updated in this SAP.

Section in this SAP	Description	Change from the protocol
2.2	Efficacy variables	Removed: Seizure-free days
2.2.3	Other efficacy variables	Removed: Time to return to baseline 28-day observable focal-onset seizure count during the 12 week Maintenance Period
Table 2-1:	Schedule of Assessments	Added Setting (Required Onsite) column to include data that may be collected through phone or video calls for visit, during the pandemic.
3.5.5	Per Protocol Set	Due to early termination of the study, PPS will not be included in the study. Removed: The Per Protocol Set (PPS) is a subset of the FAS, consisting of those subjects who had at least 1 post-Baseline efficacy measurement and who had no major protocol deviation affecting the primary efficacy variable, as confirmed during a pre-analysis data review meeting, conducted prior to study unblinding.
3.10	COVID-19 eCRF	Added, see section 3.10 for details

4.3.1	Sequential Analyses	Removed all text associated with China region due to no patient enrollment and due to early termination of the study.
4.8	Examination of subgroups	Removed: subgroup by region, gender, age Added: Levetiracetam/Brivaracetam use at study entry (Y/N) based on AED medication CRF.
6.2	Other Baseline characteristics	Removed text associated with China region.
8.1.2.2	Supportive and sensitivity analyses for the primary variable for submission to the US FDA, PMDA, and other regulatory authorities not referencing EMA	Removed text related to sensitivity analyses due to changed scope of the study.
8.1.2.4	Supportive and sensitivity analyses for the primary variable for submission to the EMA and regulatory authorities who reference EMA.	Removed text related to sensitivity analyses due to changed scope of the study.
8.1.3	Analysis of primary efficacy variable for submission to the CFDA	Removed text associated with China region.

3.10 COVID-19 eCRF

A new COVID-19 eCRF, to evaluate the impact of global pandemic was created and implemented to collect the information on impacted visit, impact category, and relationship to COVID-19.

Summary and listing (see Section 12 for details) to describe the impact on the interpretability of efficacy and safety endpoints will be performed to assess the impact of the changes on the planned analyses due to COVID-19.

4 STATISTICAL/ANALYTICAL ISSUES

General statistical and analytical issues are provided in the following sections.

4.1 Adjustments for covariates

The primary and selected efficacy analyses will be adjusted for baseline log-transformed seizure frequency and for the stratification factors:

- Current use of AEDs with binding to SV2A proteins (LEV and/or brivaracetam): Yes or No
- Geographical Region: Investigative sites have been identified in the following regions and countries at the time of this SAP amendment. More regions and/or countries may be identified and will be included in the analyses in accordance to the randomization strata:
 - Europe (Australia, Austria, Belgium, Bosnia and Herzegovina, Bulgaria, Croatia, Czech Republic, Denmark, Estonia, Finland, France, Germany, Greece, Hungary, Ireland, Italy, Netherlands, Norway, Poland, Portugal, Romania, Serbia, Slovakia, Spain, Sweden, Switzerland, Turkey, and United Kingdom)
 - North America (Canada, Mexico, and United States)
 - Japan

To ensure at least 5 subjects in each region in the FAS at each treatment group, Japan will be pooled with North America to form a non-Europe region for the efficacy analyses.

4.2 Handling of dropouts or missing data

4.2.1 Handling of missing data in seizure frequency

Unless noted otherwise, the imputation described below will be applied to seizure frequency. The responder status will be determined based on the imputed seizure frequency data. Sensitivity analyses for missing data are described in Section 8.1.2 for the primary efficacy variable.

4.2.1.1 Missing data caused by missing seizure diary

Seizure frequency will be computed over non-missing diary days. Diary compliance evaluation is described in Section 7.2.

If seizure type is known but the number of seizures is unknown, the number of seizures will be imputed using the median for the same seizure type (daily seizure number > 0) during the same analysis period (baseline or treatment period). Otherwise, the missing seizure number will be imputed using the count of next higher level of seizure type.

4.2.1.2 Missing seizure data caused by discontinuation

- Seizure frequency by analysis period:

For subjects who prematurely discontinued during the Treatment Period, the calculation of 28-day adjusted seizure frequency over the Treatment Period will be based on available seizure diary up to the end of the Treatment Period.

If a subject had less than 14 days of seizure data during the Titration and Stabilization Period, seizure frequency during the Treatment Period will be calculated based on the last 28 days with seizure data, including the data in the Baseline Period. For subjects who prematurely discontinued the study, the following methods will be applied to obtain a seizure frequency estimate for the Maintenance Period:

- Subjects who discontinued during the Titration and Stabilization Period: If a subject had at least 14 days of seizure data, seizure frequency will be calculated using all available data in the Titration and Stabilization Period and carry forward for the Maintenance Period. If a subject had less than 14 days of seizure data, seizure frequency will be calculated based on the last 28 days with seizure data, including the data in the Baseline Period and carry forward for the Maintenance Period.
- Subjects discontinued during the Maintenance Period: If a subject had at least 28 days of seizure data during the Maintenance Period, seizure frequency will be calculated using all available data in the Maintenance Period. If a subject had less than 28 days of seizure data during the Maintenance Period, seizure frequency will be calculated based on the last 28 days with seizure data, including the data in the Titration and Stabilization Period.

4.2.2 Handling of missing data for adverse events and concomitant medications

For analyses of AEs and concomitant medication usage, a complete date must be established to correctly identify the AE or medication as occurring during treatment or not. In the event of completely missing dates, or if ambiguity or incomplete data makes it impossible to determine whether a medication was concomitant, or an adverse event was treatment emergent, the medication will be considered as concomitant or the adverse event will be considered treatment emergent.

For purposes of imputing missing components of partially-reported start and stop dates for AEs and for medication use, the algorithms listed below will be followed. Start and stop dates of AEs or concomitant medication will be displayed as reported in the subject data listings (i.e., no imputed values will be displayed in data listings).

Partial AE and concomitant medication start dates will be imputed as described in the following sections.

4.2.2.1 Imputation of Partial Start Dates

- If only the month and year are specified and the month and year of first dose of IMP is not the same as the month and year of the start date, then use the 1st of the month
- If only the month and year are specified and the month and year of first dose of IMP is the same as the month and year of the start date, then use the date of first dose of IMP

- If only the year is specified, and the year of first dose of IMP is not the same as the year of the start date, then use the 1st of January of the year of the start date
- If only the year is specified, and the year of first dose of IMP is the same as the year of the start date, then use the date of first dose
- If the start date is completely unknown and the stop date is unknown or not prior to the date of first dose of IMP, then use the date of first dose of IMP.
- If the imputed start date is after the known stop date, set the start date to be the same as the stop date.

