## Concomitant epilepsy treatment

8. Subject is currently treated with an individually optimized and stable dose of at least 1 and up to 3 AEDs for the 8 weeks prior to the Screening Visit (Visit 1) with or without additional concurrent vagus nerve stimulation (VNS) or other neurostimulation treatments. The latter will not be counted as AEDs for the purpose of eligibility.

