4.8 Examination of subgroups

The primary efficacy variable will be evaluated for subgroups of interest including:

- Use of AEDs with binding to synaptic vesicle 2A (SV2A) proteins (levetiracetam [LEV] or brivaracetam [BRV], Y/N) based on stratification CRF.
- Levetiracetam/Brivaracetam use at study entry (Y/N) based on AED medication CRF.

These evaluations will be descriptive; no statistical testing of treatment-by-subgroup interactions nor statistical testing of treatment effects within subgroups will be carried out. No subgroup evaluations are planned for safety variables.

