6.4.1 AED medications

Each concomitant medication will be classified as either an AED or a non-AED medication. AED medication taken and stopped prior to the Visit 1 will be reported on the History of Previous Antiepileptic Drug Treatment CRF. AED medication that started prior to Visit 1 and which is ongoing or AED medication prescribed during the study will be recorded on the AED Medication CRF.

- Previous AEDs are AEDs taken and stopped prior to the Visit 1. Previous AEDs are reported on History of Previous Antiepileptic Drug Treatment CRF.
- AEDs taken at study entry are reported on AED CRF and if:
 - (start date of medication) < (the date of Visit 1) and (stop date of medication) \geq (the date of Visit 1) or ongoing
- Prior AEDs include both previous AEDs and AEDs taken at study entry
- Concomitant AEDs are reported on AED CRF and if:
 - (start date of medication) \leq (stop date of IMP) and (stop date of medication) \geq (start date of IMP) or ongoing
 - start date of medication is unknown but (stop date of medication) \geq (start date of study drug) or ongoing.

The number and percentage of subjects taking AED medications will be summarized by chemical/therapeutic/pharmacological subgroup (ATC classification level 4), and preferred drug name. The following summaries of AED medications will be produced for the FAS by treatment group and overall:

- Previous AEDs from the History of Previous Antiepileptic Drug Treatment CRF
- Number of previous AEDs taken: <4, 4-5, 6-7, 8-10, >10 AEDs.
- Previous AEDs by reason for AED discontinuation: The number and percentage of subjects by reason for discontinuation of previous AEDs will be summarized. Percentages for each reason for discontinuation will be relative to the number of subjects taking each AED.
- AEDs taken at study entry
- Number of AEDs taken at study entry: 1, 2, 3, and >3AEDs
- Prior AEDs
- Number of prior AEDs: <4, 4-5, 6-7, 8-10, >10 AEDs.

- Concomitant AEDs

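### An ongoing AED with a wholly unknown start, or a year-only start in the year of first dose, is dated after Visit 1 and so drops out of the study-entry and prior-AED counts and the CRF-based LEV/BRV subgroup

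*SAP*

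**What the plan says.** SAP 4.2.2 sets the scope of the date rules: for missing parts of "partially-reported start and stop dates for AEs and for medication use, the algorithms listed below will be followed". It makes no exception for AEDs.

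SAP 4.2.2.1 then handles a start known only to the year in two ways. If "the year of first dose of IMP is the same as the year of the start date, then use the date of first dose". Where the years differ, "then use the 1st of January of the year of the start date". The first-dose date is also used in a further case: "If the start date is completely unknown and the stop date is unknown or not prior to the date of first dose of IMP".

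SAP 6.4.1 classifies AEDs. To count as taken at study entry, an AED on the AED Medication CRF must satisfy "start date of medication) < (the date of Visit 1" and must be ongoing or have stopped on or after Visit 1. The next definition builds on this one: "Prior AEDs include both previous AEDs and AEDs taken at study entry". Previous AEDs, meaning those stopped before Visit 1, come from a separate CRF page and face no start-date test.

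SAP 4.8 lists two LEV/BRV subgroups for the primary variables. One uses the stratification CRF. The other is "Levetiracetam/Brivaracetam use at study entry (Y/N) based on AED medication CRF".

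Protocol 6.1, criterion 8, requires that the subject be on a "stable dose of at least 1 and up to 3 AEDs for the 8 weeks prior to the Screening Visit (Visit 1").

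**The concern.** Moving an uncertain start to the first dose is a cautious choice for an adverse event, because the event is then counted as treatment-emergent. For a drug the subject was already taking at screening, it places the start after the cut-off that defines study entry. The drug is then reported only as a concomitant AED that began on Day 1.

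Three outputs are exposed:

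- **The CRF-based LEV/BRV subgroup.** SAP 8.1.2.5 repeats both primary analyses in it, with model estimates and 95% CIs. A true user whose LEV or BRV record has such a date is placed among the non-users. The resulting disagreement with the stratification-based subgroup could be misread as a stratification error.
- **The number of prior AEDs.** Protocol 6.1, criterion 7, requires at least 4. An eligible subject can be tabulated as having fewer than 4.
- **The number of AEDs at study entry.** The categories are 1, 2, 3 and more than 3, so a subject whose only AED is moved to Day 1 has no cell.

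**Working it through.** **Inputs.** Visit 1 to Visit 2 is 4 weeks (Protocol 5.1; SAP 2.5.1). First dose is generally taken at Visit 2, Day 1 (SAP Table 3-1). The background regimen is stable for 8 weeks before Visit 1 (Protocol 6.1, criterion 8). The date rules and the study-entry test are those of SAP 4.2.2.1 and 6.4.1.

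**Step 1: gap between cut-off and imputed date.** 4 × 7 = 28 days. This matches the schedule: Day -28 to Day 1, with no Day 0, is 28 days.

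**Step 2: how far the imputed date is from a possible one.** An AED that meets the stability rule started at least 8 × 7 = 56 days before Visit 1. That is 56 + 28 = 84 days before first dose, or 81 if Visit 2 is 3 days early, as its window allows.

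**Step 3: apply the rules.** Assume Visit 1 on 2 September 2019, first dose on 30 September 2019 and an ongoing AED.

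| Recorded start | Start used | Before Visit 1? |
|---|---|---|
| 10 March 2012 | 10 March 2012 | yes |
| 2012 only | 1 January 2012 | yes |
| 2018 only | 1 January 2018 | yes |
| January 2019 | 1 January 2019 | yes |
| 2019 only | 30 September 2019 | **no** |
| wholly unknown | 30 September 2019 | **no** |

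Only the last two rows fail.

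**Step 4: reach of the same-year rule.** It can catch only an AED begun in the calendar year of first dose. The longest such an AED can have been taken at Visit 1 is about 337 days. Since an eligible background AED began at least 84 days before first dose, the rule cannot touch one when first dose falls before about 25 March. A drug taken for years is lost only if its start is wholly unknown.

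**Step 5: the month-and-year rule.** This also uses first dose when the months coincide. A start at least 81 days earlier cannot share a calendar month of at most 31 days with first dose, so an AED meeting the stability rule is never affected.

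**Step 6: effect on the counts.** Each lost AED lowers both counts by 1. With 3 previous AEDs and 1 ongoing, the true values are 3 + 1 = 4 prior AEDs and 1 at entry. The rule gives 4 − 1 = 3 (the below-4 category) and 1 − 1 = 0 (no category).

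**Step 7: does another clause restore the AED?** No. The unknown-start clause in 6.4.1 belongs to the concomitant definition only. The default in 4.2.2 for undeterminable dates is also concomitant status. If 6.4.1 were run on raw dates, an unknown start still could not satisfy the inequality. Background AEDs and AEDs prescribed in-study share one CRF page, so the date is the stated discriminator.

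**The case against.** Section 4.2.2 is written to decide whether an event or medication occurred during treatment, and for that purpose the first-dose rule is conventional. On this view the fault is a gap in the study-entry definition. That stands, and it is why the repair belongs in 6.4.1. But the SAP applies the rule to all medication use, and followed exactly it misclassifies the drug.

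The consequences are also limited. The primary ANCOVA and logistic models adjust for SV2A use as a stratification factor (SAP 4.1) and use no AED start date. The subgroup evaluations are descriptive, with no interaction or within-subgroup tests (SAP 4.8). Eligibility on prior AEDs is judged by the investigator from records and interview, not from this table. Listings show dates as reported. All of this stands.

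A reader might infer more than the text supports:

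- *That every year-only start is moved to first dose.* Only those in the year of first dose are.
- *That both LEV/BRV subgroups are distorted.* The stratification-based one uses no start date.
- *That a below-4 entry shows an ineligible subject.* It can arise from the date rule alone.
- *That a count of affected subjects can be given.* It would need the rate of unknown or same-year year-only starts, which neither document reports. Nor can the planned 400 be assumed as the denominator, because the SAP was amended for early termination.

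**Conclusion.** The point holds in a narrow form. An ongoing background AED whose start is wholly unknown, or known only to the calendar year of first dose, is dated about 28 days after Visit 1. For a drug that meets the stability criterion, that is at least 84 days too late on the nominal schedule. It then leaves the study-entry count, the prior-AED count and, if it is LEV or BRV, can leave its user among the non-users in the CRF-based subgroup.

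This rests on first dose being at Visit 2 as scheduled, and on the 4.2.2.1 rules feeding the 6.4.1 definitions, as 4.2.2 states. The number of subjects affected is unknown and could be zero. No primary estimate, p-value or multiplicity step changes. It is still worth correcting: the subgroup was added in the SAP amendment and carries estimates and CIs for both primary variables, and the prior-AED table describes the population the trial set out to study.

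**What to change.** Change SAP 6.4.1 so that the first-dose imputation is not used to decide study-entry or prior status:

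- Count an AED on the AED Medication CRF with a wholly unknown start as taken at study entry if it is ongoing or stopped on or after Visit 1, unless it is recorded as started during the study.
- For this classification only, impute a year-only AED start in the year of first dose to 1 January of that year.

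Leave the adverse-event rules and concomitant status as they are. Leave the month-and-year rule alone too: it cannot affect an AED meeting the stability criterion, and replacing it with the first of the month could create errors. With Visit 1 on 2 September and first dose on 30 September, an AED added in mid-September and recorded only as September would be dated 1 September and counted at entry.

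The cost is a few lines of SAP text and one derivation. The downside is that an AED started in-study with only the year recorded would be counted at entry; this should be rare.
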